4.1 General Description

This is a single center, exploratory, open-label, single-arm design study of 12 patients. Treatment naïve and treatment refractory patients with LP will be treated with INCB018424 PHOSPHATE CREAM. Patients who are non-responders, to physician choice standard of care, will undergo a washout period and will be enrolled in the study.

Multiple safety studies have been conducted with INCB018424 PHOSPHATE CREAM (see Safety) and a dose of 1.5% cream BID on up to 20% BSA is deemed safe. (Investigator's Brochure) The Within each cohort, the maximum reduction from baseline in the total psoriasis lesion assessment scores for the treated lesions was observed at the end of treatment (Day 28). (Investigator's Brochure) Therefore, we propose a single center, exploratory, open-label, single-arm design study of 12 patients. Treatment naïve and treatment refractory patients with LP will be treated with INCB018424 PHOSPHATE CREAM.

Individuals with LP involving less than 20% of the BSA will be eligible. Individuals must have 4 lesions at baseline, however, a minimum of 10 lesions is ideal, which are at least 5mm in diameter. 10 lesions are ideal as 2 lesions will be index lesions and 8 or more lesions will be selected from as responsive or non-responsive at 4 weeks. All lesions except for one index lesion will be treated and all lesions will be annotated, photographed, and scored. The rationale for a minimum of 8 lesions is based upon the assumption of a 50% response rate at 2 weeks. With 8 lesions, there would be a less than 1% chance that all 8 lesions would respond. Ideally, the 2 index lesions will be 10mm in diameter but this is not a requirement. Prior treatment will be allowed; however, a washout period of 2 weeks for topical and 4 weeks for systemic agents is required. At the washout period, individuals will undergo evaluation with a PGA, BSA calculation, and have the 2 largest, representative lesions selected for evaluation using a modified CAILS score lesion A- treatment index lesion and B-index control lesion. The determination of which lesion receives treatment and which is a control will be determined randomly. The additional lesions will be photographed, measured, scored, and recorded with Modified CAILS scores as well. The later calculations will be used for the determination of responsive and non-responsive lesions. Additional Pruritus measures using the NRS and Skindex-16 will be collected at that time.

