Individuals will then initiate treatment on all lesions of LP BID and will be evaluated weekly and assessed by PGA, BSA, lesion count; Modified CAILS, Pruritus NRS, and Skindex-16 between weeks 0-4 (see Appendix). Week 4 will be the primary endpoint; however therapy will be continued for an additional 4 weeks. Therapy will be stopped and the individuals will be evaluated at week 8 and assessed by PGA, BSA, lesion count, Modified CAILS, Pruritus NRS, and Skindex-16. Laboratory and safety monitoring will occur at weeks 1, 2, 3, 4, and 8, and 12. 3D Photographs will be taken at weeks 0, 1, 2, 3, 4, 8, and 12. Individual lesions will be circled at that time and the exact volume of each lesion will be measured. Up close photos will be taken of the disease and normal tissues attained at weeks 0 & 4.

Tissue will be collected for RNA sequencing at week 0 and 4. Blood collection will include the isolation at week 0, 2, and week 4, 5mL vials of blood which will be separated and the serum and cell pellet will be stored for future analysis. Five skin biopsies will be taken during the study. At week 0, up to two 3mm tissue biopsies will be taken from lesional skin and one biopsy will be taken from normal appearing skin. The initial biopsy of lesional tissue and control will be

annotated. At week 4, up to two 3mm biopsies will be taken from lesional responsive tissue and lesional refractory tissue. Responsive and non-responsive lesions will be determined by the change in Modified CAILS between week 0 and 4. Responsive will require a 50% reduction in Modified CAILS and non-responsive can have progression, no change, or up to a 50% reduction in Modified CAILS. The lesions will be chosen using full body photographs taken at week 0. Up to 60 samples will be snap frozen and stored in the tissue biobank. Once completed, RNA sequencing will be performed on the 60 tissue samples and analysis will be performed. Paired analysis of treatment responsive and refractory lesions will be made as well as treated and untreated lesions.

Nucleic Acid Extractions: RNA will be extracted from a total of 50 um of fresh tissue using the Qiagen FFPE RNeasy Micro extraction Kit according to manufacturer's recommendation.

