RNA Transcriptome Sequencing: RNA transcriptome sequencing will be carried out using commercially available techniques. Briefly, RNA Libraries will be created using up to 100ng of RNA as starting material using the Agilent RNA Access Library kit according to manufacturer's recommendation. Libraries will be QCed for quality and quantity using the Agilent BioAnalyzer High Sensitivity Chip. Pair-End sequencing will then be carried out on the Illumina HiSeq 4000 using 101bp insert fragments.

Primary and Secondary Measures:

All efficacy assessments will be performed prior to the administration of study treatment at each visit. The recommended order and the overall outline of measurements for the efficacy assessments are described below.

Efficacy measures: PGA, BSA, Modified CAILS, Pruritus NRS, Skindex-16

To determine the efficacy of INCB018424 PHOSPHATE CREAM as measured by the change in Modified CAILS score of the index treatment and control lesion (weeks 0 and 4) and changes in lesion count (week 0 and 4)

Secondary Outcome Measures: To determine the efficacy of INCB018424 PHOSPHATE CREAM and the duration of response after discontinuation as measured by the change in Pruritus NRS, (week 0 to week 4, week 0 to week 8, weeks 4 to 8, weeks 8 to 12), Change in Skindex-16 (week 0 to week 4, weeks 4 to 8, weeks 8 to 12), Change in Physician Global Assessment (PGA) (week 0 to week 4, week 0 to week 8, weeks 4 to 8, weeks 8 to 12), Change in BSA (week 0 to week 4, week 0 to week 8, weeks 4 to 8, weeks 8 to 12), Change in Modified CAILS (week 0 to week 8, weeks 4 to 8, weeks 8 to 12).

Exploratory Outcome Measures: To predict responses and examine the pharmacodynamics of treatment through the identification of unique biomarkers and transcriptomic changes of LP at week 0 and utilizing RNA sequencing on responsive and non-responsive tissue at week 4 to correlate these biomarkers with measures of global response: Modified CAILS, PGA, BSA, and lesion count.

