4.3 Duration of Participation

The study consists of 3 epochs: screening/washout period (of at least 1 week and up to 4 weeks), treatment epoch (of 8 weeks from screen/washout), and follow up epoch (of 4 weeks). The screening and washout period will allow for treatment naïve/ new diagnosis LP to undergo evaluation and diagnosis and for treatment refractory to undergo a washout. The total duration of the study will be 13-16 weeks.

Tables:

• **Table-1: Prohibited treatment**

Prohibited treatments^{†, ‡}	Washout period (before Randomization Visit)
Any concomitant oral or topical JAK inhibitor	Prohibited
Any biologic drug	Stable dose for 3 months
Immunomodulation treatments for LP [§] [e.g., methotrexate, cyclosporine A, corticosteroids (oral, i.v., intramuscular, s.c., intra-articular, transdermal), mycophenolate mofetil, azathioprine]	4 weeks
Topical treatment that is likely to impact signs and symptoms of LP (e.g., pimecrolimus, tacrolimus)	2 weeks
Non-immunosuppressive agents (tetracycline antibiotics & niacinamide)	2 weeks
Prohibited regimen of Topical Corticosteroids (TCS)	
TCS on any location on body (including face, scalp and/or genitoanal area)	2 weeks

[†] If the prohibited treatment is being used during the study for any indication, the subject must discontinue use of the prohibited treatment if he/she wishes to continue in the study.

[‡] In case of undue safety risk for the subject, the subject should discontinue study treatment at the discretion of the investigator/qualified site staff. If the subject received a live virus vaccination during the study, the subject must discontinue study treatment.

[§]Inhalative CS with only a topical effect (e.g., to treat asthma) are not considered “systemic immunomodulation treatments” and are therefore acceptable as co-medication. Immunosuppressive medication for conditions other than LP will be allowed.

Table-2: Screening and Visits (+/- 2 day window)

	Screening	Day 0	Week 1	Week 2	Week 3	Week 4	Week 8	Week 12

INCB18424		X	X	X	X	X		
Physical Exam	X	X	X	X	X	X	X	X
Adverse Event Assessment		X	X	X	X	X	X	X
Chest X-ray	X							
Assessments: PGA, BSA, lesional number, Modified CAILS, Skindex-16, Pruritus NRS		X	X	X	X	X	X	X
Photographer		X	X	X	X	X	X	X
Skin Biopsy (tissue/serum bank)		X				X		
Urine Pregnancy Test	X							
Venipuncture	X	X	X	X	X	X	X	X
Biomarker/RNAseq blood (tissue/serum bank)		X		X		X		
CMP	X		X	X	X	X	X	X
CBC	X		X	X	X	X	X	X
Quantiferon Gold	X							
Hepatitis B	X							
Hepatitis C	X							

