6.7.4 Return or Destruction of Study Drug

At the completion of the study, there will be a final reconciliation of drug shipped, drug dispensed, drug returns, and drug remaining. This reconciliation will be logged on the drug reconciliation form, signed and dated. Any discrepancies noted will be documented and investigated, prior to return or destruction of unused study drug. Drug destroyed on site will be documented in the study files.

7 Study Procedures

7.1 Visit 1

Screening visit:

During this visit, we will do some tests and procedures to see if subjects are eligible to take part in this research study. The study staff will review the results of these tests and procedures. If subjects aren't eligible, the Principal Investigator will tell them why. At this visit we will:

- Ask about medical history
- Perform a physical exam, including height, weight, and “vital signs” (blood pressure, temperature, heart and breathing rates)
- Perform a chest x-ray
- Draw a blood sample
- We may take swabs to test for certain fungal and bacterial infections
- Test urine for pregnancy if female subject is able to become pregnant

If it isn't known if subject has HIV, Hepatitis B or C, blood tests will need to be done.

7.2 Visit 2

Day 0 Visit we will:

- Perform a physical exam, check vital signs and ask about side effects or health problems since last visit
- Exam skin lesions to note any changes
- Take photographs of skin lesions to document any changes
- Draw a blood sample
- Perform a skin biopsy (up to 3 tissue samples will be taken)
- Perform a tap stripping on skin
- Dispense study drug

7.3 Visit 3

Week 1 Visit we will:

- Perform a physical exam, check vital signs and ask about side effects or health problems since last visit
- Exam skin lesions to note any changes
- Take photographs of skin lesions to document any changes
- Draw a blood sample
- Dispense study drug

7.4 Visit 4

Week 2 Visit we will:

- Perform a physical exam, check vital signs and ask about side effects or health problems since last visit
- Exam skin lesions to note any changes
- Take photographs of skin lesions to document any changes
- Draw a blood sample
- Dispense study drug

7.5 Visit 5

Week 3 Visit we will:

- Give subject a physical exam, check vital signs and ask about side effects or health problems since last visit
- Exam skin lesions to note any changes
- Take photographs of skin lesions to document any changes
- Draw a blood sample
- Dispense study drug

7.6 Visit 6

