Appendix:

Physician Global Assessment: (9, 10)

Grade 0 Completely clear: no evidence of disease (100% improvement) CCR

Grade 1 Almost clear: very significant clearance ($\geq 90\%$ to $< 100\%$) PR

Grade 2 Marked Improvement: significant improvement ($\geq 75\%$ to $< 90\%$) PR

Grade 3 Moderate improvement: intermediate between slight and marked ($\geq 50\%$ to $< 75\%$) PR

Grade 4 Slight improvement: some improvement ($\geq 25\%$ to $< 50\%$); however, significant evidence of disease remains SD

Grade 5 No change; disease has not changed from baseline condition ($\pm < 25\%$) SD

Grade 6 Worse, disease is worse than at baseline evaluation by ($\geq 25\%$) or more PD

CCR- Complete clinical response

PR- Partial response

SD- Stable disease

PD- Progressive Disease

Modified CAILS-**Clinical Assessment Scale of Severity for Index Lesion Signs and Symptoms (CAILS) (9, 10)**

Scale	Grade
0	No evidence of sign or symptom
1	Intermediate interval
2	Mild: less than average presentation of sign or symptom
3	Intermediate interval
4	Moderate: average disease presentation of sign or symptom
5	Intermediate interval
6	Severe: greater than 25% worse than average severity of sign or symptom
7	Intermediate interval
8	Very severe: the near worst severity sign or symptom

A scale of 0 to 18 was used to grade lesion size by square centimeter (0, 0 [no measurable area]; 1, >0 and ≤4; 2, >4 and ≤10; 3, >10 and ≤16; 4, >16 and ≤25; 5, >25 and ≤35; 6, >35 and ≤45; 7, >45 and ≤55; 8, >55 and ≤70; 9, >70 and ≤90; 10, >90 and ≤110; 11, >110 and ≤130; 12, >130 and ≤155; 13, >155 and ≤180; 14, >180 and ≤210; 15, >210 and ≤240; 16, >240 and ≤270; 17, >270 and ≤300; and 18, >300). The area of the lesion will be measured with digital planimetry. (9-11)

Modified CAILS index lesion score:

1. Erythema(0-8)
 2. Scaling (0-8)
 3. Plaque elevation (0-8)
 4. Size (0-18)
 - o Trained clinical evaluators assessed the same patients throughout the study.
 - o The CA (the ratio of summation (Σ) of all clinical signs for these index lesion at each visit compared with baseline) included cutaneous tumors and all extra cutaneous manifestations of disease.
 - o Complete clinical remission (CCR) required a CA ratio of 0 with no evidence of disease
 - o Partial remission (PR) was defined as
 - o A CA ratio of 0.5 or lower without new clinically abnormal lymph nodes
 - o Progressive disease was defined as
 - o A 25% or higher increase in CA ratio
- (Olsen et al., 2011b, Duvic et al., 2001b)

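### The recommended assessment order lists the itch and quality-of-life questionnaires after the physician's gradings, which leaves open an avoidable cue to subjects' ratings in an open-label trial

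*Combined protocol and SAP*

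**What the plan says.** The design is stated in section 4.1: "This is a single center, exploratory, open-label, single-arm design study of 12 patients".

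Under Primary and Secondary Measures in the same section, the protocol announces a sequence: "The recommended order and the overall outline of measurements for the efficacy assessments are described below". The list of instruments that follows is "Efficacy measures: PGA, BSA, Modified CAILS, Pruritus NRS, Skindex-16". The first three are the physician's assessments and the last two are the subject's.

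Two other places name the same instruments:
- The visit narrative in section 4.1 has subjects "assessed by PGA, BSA, lesion count; Modified CAILS, Pruritus NRS, and Skindex-16 between weeks 0-4", and it repeats that sequence for week 8.
- Table-2 in section 4.3 has a single row, "Assessments: PGA, BSA, lesional number, Modified CAILS, Skindex-16, Pruritus NRS". The two questionnaires change places there but still come last.

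The other timing rule for these measures is "All efficacy assessments will be performed prior to the administration of study treatment at each visit". Sections 7.2 to 7.8 list the examination, photographs, blood draw and, on Day 0 and at Week 4, the biopsies (for Day 0: "Perform a skin biopsy (up to 3 tissue samples will be taken)"). They do not name the questionnaires.

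The PGA in the Appendix is a scale of change from baseline, with entries such as "Grade 2 Marked Improvement: significant improvement".

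**The concern.** Pruritus NRS and Skindex-16 are ratings of the whole subject. The untreated index lesion gives Modified CAILS a comparator within the subject, but itch and quality of life have none. Whatever shifts those ratings other than the drug is therefore read as drug effect.

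If the subject rates itch straight after a physician has examined the lesions and judged improvement, the manner or outcome of that examination can colour the rating. On Day 0 there is no improvement to convey, so such an influence would enter later scores and not the baseline.

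Section 8.2 says the study is for estimation only and is meant to supply effect sizes for planning later studies. What is at stake is bias in an itch or quality-of-life estimate that may be carried forward. No test decision hangs on it.

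**Working it through.** **1. Is the order as described?** The places that name the instruments, side by side:

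| Place | Physician measures | Subject-reported measures |
|---|---|---|
| 4.1, efficacy measures list | PGA, BSA, Modified CAILS | then NRS, Skindex-16 |
| 4.1, visit narrative | PGA, BSA, lesion count, Modified CAILS | then NRS, Skindex-16 |
| Table-2 | PGA, BSA, lesion number, Modified CAILS | then Skindex-16, NRS |
| 7.2 to 7.8 | lesion examination only; scales not named | not named |

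The questionnaires come last wherever they are listed, and nothing reverses this.

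**2. Which endpoints are exposed?** Section 4.5 has 4 NRS + 3 Skindex-16 + 4 PGA + 4 BSA + 3 Modified CAILS = 18 secondary contrasts. Of these, 4 + 3 = 7 are subject-reported.

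**3. In which of the 7 does a cue survive?** Write the observed score at week t as the uncued score plus c(t), and suppose c(0) = 0 and c(t) = c at every later visit. The bias in a contrast from week s to week t is c(t) − c(s).

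| Contrast | Bias |
|---|---|
| NRS 0–4 | c |
| NRS 0–8 | c |
| Skindex-16 0–4 | c |
| NRS 4–8, NRS 8–12 | c − c = 0 |
| Skindex-16 4–8, Skindex-16 8–12 | c − c = 0 |

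A constant cue biases 3 contrasts and cancels in 4. It would remain in those 4 only as far as it differed between visits, and the documents give no basis for sizing that.

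**4. How large could it be?** The documents give neither an SD for NRS change nor any figure for a cue, so this is illustration only. Assume an SD of 2.5 points (range 2 to 3). With n = 12, SE = SD/√12 = 2.5/3.464 = 0.72 (0.58 to 0.87). The rejection rate of a two-sided 5% paired t test with 11 df when there is no drug effect would be:

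| Assumed cue | SD 2 | SD 2.5 | SD 3 |
|---|---|---|---|
| 0.5 points | 12.4% | 9.7% | 8.3% |
| 1 point | 35.3% | 24.5% | 18.4% |

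The plan names Wilcoxon tests and a mixed model, states no alpha, and is for estimation. The table therefore shows only that a cue of about one SE (1 point is 1/0.72 = 1.4 SE) would not be trivial. It is not evidence that such a cue exists.

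**5. Biopsies.** Up to 3 samples are taken on Day 0 and up to 2 at Week 4. Sections 7.2 and 7.6 list dispensing after the biopsy, so the rule about assessing before treatment is met whether the questionnaires come before or after it. The sequence is simply not fixed.

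**The case against.** The evidence for a sequence is thin. It is one unnumbered line, described only as recommended. It omits lesion count, which section 4.4 makes a primary endpoint, and Table-2 orders the two questionnaires differently. A fair alternative reading is that an order is promised and never properly specified. That stands, but the gap it describes has the same remedy.

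A reader might infer that subjects are told their grades before they rate themselves. The documents do not say so. The Appendix describes trained evaluators and digital planimetry and is silent on disclosure.

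A reader might also infer that all 7 subject-reported contrasts are biased. Only 3 use week 0, and a constant cue drops out of the other 4.

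A reader might infer that biopsy discomfort is planned to precede the questionnaires. It is not. Table-2 lists the assessments above the biopsy, and at Week 4 the biopsy sites depend on the change in Modified CAILS, so at least that grading must come first. Sections 7.2 to 7.8 do not name PGA, BSA or Modified CAILS either, so the questionnaires' absence there says nothing about their timing. With biopsies at both Day 0 and Week 4, any discomfort would also partly offset in the 0–4 contrast.

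Finally, the gain is limited. Subjects know they are using active drug, apply it twice daily and see their own skin. A different order changes none of that. This objection stands in full and keeps the point minor.

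**Conclusion.** The point holds as a minor design improvement. The protocol's own recommended list, its visit narrative and Table-2 all put the subject-reported measures after the physician's assessments, and nothing requires the reverse. In an open-label, single-arm trial with a PGA graded as improvement, this leaves open a risk that the examination cues ratings after Day 0.

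The risk bears mainly on NRS 0–4, NRS 0–8 and Skindex-16 0–4. That count assumes no cue on Day 0 and a constant one afterwards. The primary endpoints, Modified CAILS and lesion count, are not affected. The size of any bias is unknown, and the rejection rates shown rest wholly on assumed SDs and cues and on a test the plan does not name. The documents do not support saying that the itch or quality-of-life results will be biased, only that an avoidable source of bias has not been closed.

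**What to change.** In section 4.1 and in Table-2, state that at every visit from Day 0 to Week 12 the subject completes Pruritus NRS and Skindex-16 first, before the physical examination, lesion grading and counting, photographs, blood draw and any biopsy. Use one order for the two questionnaires in both places. In Table-2 this is clearest if they get their own row above the physician's assessments. List the questionnaires as the first item in sections 7.2 to 7.8, where they are not named now.

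The cost is a sentence, a table edit and a change to visit flow. It adds no procedure, staff or subject burden. It cannot be done afterwards, because a cue of this kind cannot be separated from drug effect in the analysis.

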4.2 Number of Subjects

12 subjects will be enrolled in this study.

4.3 Duration of Participation

The study consists of 3 epochs: screening/washout period (of at least 1 week and up to 4 weeks), treatment epoch (of 8 weeks from screen/washout), and follow up epoch (of 4 weeks). The screening and washout period will allow for treatment naïve/ new diagnosis LP to undergo evaluation and diagnosis and for treatment refractory to undergo a washout. The total duration of the study will be 13-16 weeks.

Tables:

• **Table-1: Prohibited treatment**

Prohibited treatments^{†, ‡}	Washout period (before Randomization Visit)
Any concomitant oral or topical JAK inhibitor	Prohibited
Any biologic drug	Stable dose for 3 months
Immunomodulation treatments for LP [§] [e.g., methotrexate, cyclosporine A, corticosteroids (oral, i.v., intramuscular, s.c., intra-articular, transdermal), mycophenolate mofetil, azathioprine]	4 weeks
Topical treatment that is likely to impact signs and symptoms of LP (e.g., pimecrolimus, tacrolimus)	2 weeks
Non-immunosuppressive agents (tetracycline antibiotics & niacinamide)	2 weeks
Prohibited regimen of Topical Corticosteroids (TCS)	
TCS on any location on body (including face, scalp and/or genitoanal area)	2 weeks

[†] If the prohibited treatment is being used during the study for any indication, the subject must discontinue use of the prohibited treatment if he/she wishes to continue in the study.

[‡] In case of undue safety risk for the subject, the subject should discontinue study treatment at the discretion of the investigator/qualified site staff. If the subject received a live virus vaccination during the study, the subject must discontinue study treatment.

[§]Inhalative CS with only a topical effect (e.g., to treat asthma) are not considered “systemic immunomodulation treatments” and are therefore acceptable as co-medication. Immunosuppressive medication for conditions other than LP will be allowed.

Table-2: Screening and Visits (+/- 2 day window)

	Screening	Day 0	Week 1	Week 2	Week 3	Week 4	Week 8	Week 12

INCB18424		X	X	X	X	X		
Physical Exam	X	X	X	X	X	X	X	X
Adverse Event Assessment		X	X	X	X	X	X	X
Chest X-ray	X							
Assessments: PGA, BSA, lesional number, Modified CAILS, Skindex-16, Pruritus NRS		X	X	X	X	X	X	X
Photographer		X	X	X	X	X	X	X
Skin Biopsy (tissue/serum bank)		X				X		
Urine Pregnancy Test	X							
Venipuncture	X	X	X	X	X	X	X	X
Biomarker/RNAseq blood (tissue/serum bank)		X		X		X		
CMP	X		X	X	X	X	X	X
CBC	X		X	X	X	X	X	X
Quantiferon Gold	X							
Hepatitis B	X							
Hepatitis C	X							
HIV	X							
Coccidioidomycosis	X							

